11.4.3. Unanticipated Problem (UP) reporting

Incidents that meet the OHRP criteria for UPs will be reported according to the funding sponsor and IRB requirements. UPs that are SAEs will be reported to the IRB and DMC within the required reporting timelines described above)

The UP report will include the following information:

- Protocol identifying information: protocol title and number, PI's name, and the IRB project number;
- A detailed description of the event, incident, experience, or outcome;
- An explanation of the basis for determining that the event, incident, experience, or outcome represents an UP;
- A description of any changes to the protocol or other corrective actions that have been taken or are proposed in response to the UP.

11.4.4. Events of special interest

The safety data that will be reviewed includes the number and seriousness of infections, malignancies, hematological complications including leucopenia, anemia, and thrombocytopenia, cardiovascular complications and events, neurological symptoms, gastrointestinal symptoms, and immunosuppression-related adverse effects

11.4.5. Reporting of pregnancy

It is unlikely that patient will be pregnant during that period as most of the child bearing age group females are required to be on the birth control measure and are recommended not to be pregnant. If patient get pregnant during the study period, subject will be monitored through child birth and report any birth defect.

11.5. Study Halting Rules

This study may be temporarily suspended or prematurely terminated if there is sufficient reasonable cause. These subjects are at high risk for multiple complications and decision to halt the study based on SAEs will be on PI discretion. Written notification, documenting the reason for study suspension or termination, will be provided by the suspending or terminating party to investigator, funding agency and the regulatory authorities. If the study is prematurely terminated or suspended, the PI will promptly inform the IRB and DMC and will provide the reason(s) for the termination or suspension.

Circumstances that may warrant termination or suspension include, but are not limited to:

- Determination of unexpected, significant, or unacceptable risk to participants
- Demonstration of efficacy that would warrant stopping
- Insufficient compliance to protocol requirements
- Data that are not sufficiently complete and/or evaluable
- Determination of futility

11.5.1. Subject Stopping Rules

Subjects will be informed that they have the right to withdraw from the study at any time for any reason, without prejudice to their medical care. The investigator also has the right to withdraw patients from the study for any of the following reasons:

- If study drug is discontinued due to AE
- If a subject is withdrawn due to an adverse event, the dose adjustment, modification and withdrawal procedures related to adverse events will be followed and will be switched to other alternative medications..
- Protocol violation
- Lost to follow-up
- Study terminated
- Non-compliance

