6.6.5. Costs to the Subject

There is no extra cost to the patients to be enrolled in the study. Extended release Envarsus XR will be provided through the Veloxis pharmacy for the entire period of the study. Immediate release tacrolimus will fall under the SOC and will be provided through the standard medication distribution system.

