6.7.3. Data Collection and Follow-up for Withdrawn Subjects

Data for the study purpose will not be collected from subjects who have withdrawn from the study but have active treatment either with SOC tacrolimus or with study drug, Envarsus-XR.

7. Study Agent

Subjects will be randomized to receive (in a 1:1 manner) to either the standard of care arm or the experimental arm:

- Standard of Care: Immediate release tacrolimus
- Experimental: Envarsus XR

This study is exempt from the requirements of an IND based on meeting the criteria defined in the FDA information sheet "[Off-Label and Investigational Use Of Marketed Drugs, Biologics, and Medical Devices](#)".

21 CFR 312.2(b) Exemptions. (1) The clinical investigation of a drug product that is lawfully marketed in the United States is exempt from the requirements of this part if all the following apply:

- (i) The investigation is not intended to be reported to FDA as a well-controlled study in support of a new indication for use nor intended to be used to support any other significant change in the labeling for the drug;
- (ii) If the drug that is undergoing investigation is lawfully marketed as a prescription drug product, the investigation is not intended to support a significant change in the advertising for the product;
- (iii) The investigation does not involve a route of administration or dosage level or use in a patient population or other factor that significantly increases the risks (or decreases the acceptability of the risks) associated with the use of the drug product;
- (iv) The investigation is conducted in compliance with the requirements for institutional review set forth in part 56 and with the requirements for informed consent set forth in part 50; and
- (v) The investigation is conducted in compliance with the requirements of 312.7.

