7.4. Randomization and Blinding of Study Drug

This study will be a randomized, unblinded study involving extended release tacrolimus called Envarsus XR once a day and immediate acting tacrolimus twice a day.

8. Study Procedures

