9.3. Subject Population(s) for Analysis

All randomized and completed study patient data will be used for primary and secondary analysis. Primary analysis include needs for dose adjustment of the Envarsus XR or tacrolimus and secondary analysis include duration of recovery from the DGF.

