The SMS will review the accuracy and completeness of completed consent and HIPAA documents for each enrolled subject. For approximately 10-20% of enrolled subjects, the SMS will evaluate the completeness and accuracy of the data collected and conduct a comparison with the electronic data captured, resulting in electronic queries with resolution or validation. In addition, the SMS staff will verify adherence to protocol eligibility criteria, verify documentation for the accountability and administration of the study product, verify documentation of study procedures, and verify that FDA required SAE reports were appropriately submitted.

The study monitor(s) will work closely with the ICTR DMC statistician and the study statistician to conduct periodic central data reviews, with follow-up conducted by the study monitors for any data discrepancies identified.

The PI will be provided copies of monitoring reports within 30 days of visit.

Details of clinical study monitoring are documented in a SMP (Study Monitoring Plan) that can be found in Appendix 4. The SMP describes in detail who will conduct the monitoring, at what frequency monitoring will be done, at what level of detail monitoring will be performed, and the distribution of monitoring reports.

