12.2. Protocol Deviations

A protocol deviation is any noncompliance with the applicable regulations, clinical trial protocol, GCP, or MOP requirements. The noncompliance may be either on the part of the participant, the investigator, or the study site staff. As a result of deviations, corrective actions are to be developed by the site and implemented promptly.

These practices are consistent with ICH E6:

- 4.5 Compliance with Protocol, sections 4.5.1, 4.5.2, and 4.5.3
- 5.1 Quality Assurance and Quality Control, section 5.1.1
- 5.20 Noncompliance, sections 5.20.1, and 5.20.2.

The site PI/staff will be responsible for continuous vigilance to identify and report deviations to the protocol. These will be reported within 5 working days of identification of the protocol deviation, or within 5 business days of the scheduled protocol-required activity. All deviations must be addressed in study source documents. Protocol deviations will be sent to the local IRB per their guidelines. The PI and study staff are responsible for knowing and adhering to their IRB requirements. Further details about the handling of protocol deviations will be included in the MOP.

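### Section 11.5.1 lets an unblinded investigator withdraw patients from the study for undefined protocol violation or non-compliance, and Sections 6.7.3 and 9.3 then drop them from the comparison: a bias of unknown size and direction

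*Combined protocol and SAP*

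**What the plan says.** Four provisions act together.

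- **Withdrawal (11.5.1).** "The investigator also has the right to withdraw patients from the study for any of the following reasons". Among the reasons are protocol violation and non-compliance. Neither has a definition or a threshold, and the rule is not specific to an arm. What the patient leaves is the study, not only the assigned drug.
- **Blinding (7.4).** "This study will be a randomized, unblinded study involving extended release tacrolimus called Envarsus XR once a day and immediate acting tacrolimus twice a day". Section 7.1 adds that the study team makes every dose change in both arms.
- **Data after withdrawal (6.7.3).** "Data for the study purpose will not be collected from subjects who have withdrawn from the study", where those patients are still being treated with either formulation.
- **Analysis set (9.3).** "All randomized and completed study patient data will be used for primary and secondary analysis".

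Section 12.2 sets a wide definition: "A protocol deviation is any noncompliance with the applicable regulations, clinical trial protocol, GCP, or MOP requirements". The protocol does not say how a deviation differs from the violation named in 11.5.1. Section 12.4 is headed as compliance monitoring of subjects but gives no compliance measure for either arm.

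**The concern.** Randomization protects the comparison only while the patients compared are those who were randomized. Here a patient can be taken out after randomization, on a ground nobody has defined, by someone who knows the arm and can see how the graft is recovering. The primary endpoint in 5.1.1 is the time from first to last dialysis. If a patient leaves before the last dialysis, that date is never recorded for the study. Correcting the analysis set later could not restore it.

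The secondary endpoint, the number of dose adjustments, is exposed in the same way. Patients with erratic intake may well have erratic levels, and so an unusual number of adjustments.

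The loss is also avoidable. These patients have not asked to leave, and Section 10.2.1 makes the medical record and the Transplant Database the main data sources already.

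**Working it through.** **Inputs from the protocol.** Section 9.1: control mean 13.9 days, +/- 7 read as an SD; target below 10 days, so a difference of 13.9 − 10 = 3.9 days at the limit; 50 per arm, with no dropout allowance stated. Section 9.2: significance level 0.05, taken as two-sided because the sidedness is not given.

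**The plan's own figure.** No power is stated. At 80% power, two-sided:

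n per arm = 2 × (1.96 + 0.8416)² × 7² / 3.9² = 50.6, so 51.

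That agrees with 50 to within one patient. The 80% is therefore an inference.

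**Power when completers are lost.** Power = Φ(3.9 / (7√(2/n)) − 1.96).

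| Completers per arm | 3.9 / (7√(2/n)) | Power |
|---|---|---|
| 50 | 2.786 | 79.6% |
| 45 | 2.643 | 75.3% |
| 40 | 2.492 | 70.3% |

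**Bias in the mean difference.** The documents give no withdrawal rate and no outcome for such patients, so these inputs are assumed. Suppose there is no true drug effect. In each arm a share f of patients is open to removal, and their DGF duration differs from the rest by d days. If a proportion r of them is removed, the arm's mean moves, relative to the other patients, by

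m(r) = f(1 − r)d / (1 − fr).

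The bias is m in one arm minus m in the other. With full removal in one arm and none in the other, its absolute size is f × d.

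| Removed, one arm only | d = 3.5 days | d = 7 days |
|---|---|---|
| 3 of 50 (f = 0.06) | 0.21 days | 0.42 days |
| 8 of 50 (f = 0.16) | 0.56 days | 1.12 days |

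Relative to 3.9 days, the range runs from 0.21/3.9 = 5% to 1.12/3.9 = 29%.

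**Direction.** Removing slow recoverers from the Envarsus arm flatters Envarsus XR. Removing them from the standard-care arm, or removing fast recoverers from the Envarsus arm, does the reverse. With d = 0 the bias is 0. With equal removal it is 0. Partial imbalance shrinks it: for f = 0.10 and d = 7, full removal in one arm and half in the other gives 0.05 × 7 / 0.95 = 0.37 days, against 0.70 days when removal is wholly one-sided.

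**Type I error at the two ends** (normal approximation, SD held at 7):

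- 3 removed, 3.5 days: SE = 7√(1/47 + 1/50) = 1.422; 0.21/1.422 = 0.148; Φ(−1.812) + Φ(−2.108) = 0.0350 + 0.0175, or about 5.3%.
- 8 removed, 7 days: SE = 7√(1/42 + 1/50) = 1.465; 1.12/1.465 = 0.764; Φ(−1.196) + Φ(−2.724) = 0.1159 + 0.0032, or about 11.9%.

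The second figure is slightly high, because mixing two groups widens the SD in the arm that keeps them. In a t-test simulation of that case, the error in the flattering direction was 10.2%, against 11.6% here.

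**The case against.** **What stands.** A right to withdraw patients does not mean it will be used often. Planned DGF lasts about two weeks and patients are reviewed every two to three days (8.2.1), so 3 to 8 removals per 50 may be too many, and the low end of the illustration is negligible. Section 12.2 answers a deviation with correction and reporting, not withdrawal, so its wide definition does not make nearly everyone removable. The zero-day windows in 8.2.1 do not either: they do not apply to Day 1 or the monthly visits, and a footnote allows more or fewer visits. It is also fair to say that 6.7.3 and 9.3 do most of the damage; 11.5.1 supplies the discretionary route into them.

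**What stands only in part.** Section 6.7.2 asks withdrawn patients to attend one last visit. That gives a snapshot at departure. It does not give a last-dialysis date that falls later, and it sits awkwardly with 6.7.3.

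**A stronger reading that the documents do not support.** A reader might infer that non-compliance is visible only in the Envarsus arm, so that removals fall there and favour Envarsus XR. The supply routes suggest it: "Extended release Envarsus XR will be provided through the Veloxis pharmacy for the entire period of the study", whereas "Immediate release tacrolimus will fall under the SOC and will be provided through the standard medication distribution system". The Study Summary also calls only Envarsus XR the study drug. But different supply does not establish different accountability. Monitors are to "verify documentation for the accountability and administration of the study product", with no arm named, and the Study Summary row on the study product describes both formulations. Accountability is likewise not tied to an arm in 8.2.2 or in the log review in 12.1.1. Dispensing records (10.2.1) and similar laboratory tests, including tacrolimus levels (8.1), are available in both arms.

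The favourable direction also needs poor compliers to recover later. The hypothesis in 3.2 leans that way, but it is what the trial is testing, and 3.1 leaves open whether stopping a calcineurin inhibitor during DGF helps or harms.

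**Conclusion.** The concern holds as a defect of the rules. Undefined, discretionary withdrawal in an unblinded trial, no study data afterwards for patients still on either drug, and an analysis of completers together allow selective exclusion from the primary comparison. The size and direction are unknown. The shift of about 0.2 to 1.1 days is an illustration, not an estimate: it rests on assumed counts, assumed differences in duration and wholly one-sided removal, and it disappears under equal removal or unaffected duration. The power loss, from about 80% to about 75% or 70%, needs no assumption about direction, only that completers fall to 45 or 40 per arm. Neither one-sided accountability nor a bias in favour of Envarsus XR is shown. The change is still worth making, because it removes this bias whichever way it would run.

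**What to change.** Three linked amendments are needed. Changing 11.5.1 alone would contradict 6.7.2 and 6.7.3 and leave the completer analysis in place.

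1. **11.5.1.** Delete protocol violation and non-compliance as grounds for leaving the study. Record both as deviations under 12.2.
2. **6.7.2 and 6.7.3.** State that stopping the assigned drug, for any reason, does not end follow-up. Continue to take first and last dialysis dates, dose changes and adverse events from the medical record and Transplant Database to month 3, unless the patient withdraws consent or HIPAA authorization.
3. **9.3.** Make the primary analysis all randomized patients in the arm assigned. Add a per-protocol analysis as sensitivity, and report withdrawals by arm and reason.

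It would also help to state whether drug accountability covers both arms. Treatment decisions stay as they are.

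The cost is a few paragraphs of wording and a little more chart review in records the study already uses. Off-protocol patients will dilute the treatment contrast slightly; the per-protocol analysis shows how far the result depends on them.

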11.6. Safety Oversight

We will utilize the UW ICTR Data Monitoring Committee (DMC) to oversee the study. The UW ICTR DMC is comprised of experienced members with expertise required to oversee this study. In providing oversight for the conduct of this study, the ICTR DMC will meet annually in which subjects will have any study procedures. At these annual meetings, the DMC members will review protocol-specific reports created by statisticians using data pulled from both the ICTR OnCore and the ICTR REDCap systems. These standard reports will include an overview of study objectives, a review of actual and projected accrual rates, an evaluation of patient demographics, a summary of the number and seriousness of adverse events, and an analysis of the primary and secondary outcomes. An interim analysis of study results may be performed and source documents may be reviewed to allow the DMC to independently judge whether the overall integrity and conduct of the protocol remain acceptable based on data provided and reported by the Principal Investigator. The DMC will make recommendations to the Principal Investigator that could include actions of continuation, modification, suspension, or termination.

Serious adverse events will be reviewed by the DMC co-chairs once reported to the DMC. An ad hoc meeting of the DMC may be scheduled to discuss the SAE(s) and any potential action that is needed pertaining to study continuation.

12. Study Monitoring, Auditing, and Inspecting

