5.1.3. Primary Safety Endpoints

Primary safety endpoints include: infections, malignancies, hematological complications including leukopenia, anemia, and thrombocytopenia, cardiovascular complications and events, neuropathy, tremors, gastrointestinal symptoms, uncontrolled hypertension, serious electrolytes abnormalities and immunosuppression-related adverse effects.

6. Study Subjects – Enrollment and Withdrawal

- A total of 100 subjects (50 subjects in each arm) with the diagnosis of DGF will be enrolled over a period of 2 years.
- DGF is defined as the need for a dialysis within the first week of transplant. Once potential DGF patients are identified, the transplant nephrology team will be consulted and the transplant nephrology provider will perform initial evaluation of a patient, discussion with the patient about his/her interest in participating in the research study and inform the research coordinator.
- Subjects will participate in the study until the recovery of DGF as documented by the provider as “discharged from the DGF clinic” or no need for dialysis for more than one week (7 days).
- Subject would be followed for maximum of 3 months. If they still need dialysis beyond 3 months, will be declared as primary dysfunction and will disqualify from the study.

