9.2. Statistical Methods

Continuous data will be compared using Student's t-test or the Wilcoxon Rank Sum test, as appropriate, while categorical data will be analyzed using Fisher's exact test or chi-square test. P values < 0.05 will be considered statistically significant. Kaplan-Meier analyses will be performed to study graft survival if appropriate.

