9.4. Planned Interim Analysis

We will utilize the UW ICTR Data Monitoring Committee (DMC) to oversee the study and is described further in section 11.6. Source documents may be reviewed to allow the DMC to independently judge whether the overall integrity and conduct of the protocol remain acceptable based on data provided and reported by the Principal Investigator. The DMC will make recommendations to the Principal investigator that could include actions of continuation, modification, suspension or termination.

10. Data Collection, Handling and Record Keeping

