11.4. Reporting procedures

Together with the UW ICTR Data Monitoring Committee (DMC) we will develop a detailed a data and safety monitoring plan (DSMP) which will ensure ongoing safety of participating patients commensurate with the level of risk and complexity of the protocol treatment to minimize risks, integrity of trial data and scientific validity of the trial. The development of the DSMP will be guided by the NIH Policy for Data and Safety Monitoring and by the FDA Guidance on the Establishment and Operation of Clinical Trial Data Monitoring Committees. The plan will make certain that review of the conduct of research is rigorous, independent and objective, interim safety and efficacy data is collected and presented, and progress towards achieving study goals is made. It will cover policies and procedures for reporting adverse events to the DMC, IRB, and the drug manufacturer(s).

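### Annual DMC reports include the primary outcome and an efficacy stop is listed, but section 9.4 neither states nor cites a criterion, and 9.3 conflicts with 5.1.1 on which outcome is primary

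*Combined protocol and SAP*

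**What the plan says.** **Looks at the outcomes.** Under section 11.6, "the ICTR DMC will meet annually", and its standard reports will include "a summary of the number and seriousness of adverse events, and an analysis of the primary and secondary outcomes". The same section adds that "An interim analysis of study results may be performed", so that the committee can judge the integrity and conduct of the protocol. Section 11.4 expects that "interim safety and efficacy data is collected and presented, and progress towards achieving study goals is made", and 3.5.2 says much the same.

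**Power to stop.** Section 9.4 says: "The DMC will make recommendations to the Principal investigator that could include actions of continuation, modification, suspension or termination". Sections 6.7.1 and 11.5 each list, among circumstances that may justify termination, "Demonstration of efficacy that would warrant stopping".

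**Criterion.** Section 9.4 refers to 11.6. Neither gives a number or timing of looks, a boundary or an adjusted final level. The only threshold in the text is in 9.2: "P values < 0.05 will be considered statistically significant". Section 3.5.2 refers to a DMC charter and a DSMP (Appendices 2 and 3); their text is not in the supplied document.

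**Outcome.** Section 5.1.1 makes duration of DGF primary and 5.1.2 makes the number of dose adjustments secondary. The sample size in 9.1 rests on duration of DGF. Section 9.3 reverses the order: dose adjustment is the primary analysis and DGF recovery the secondary one.

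**The concern.** An efficacy stop needs a named outcome, a comparison by arm and a threshold that allows for repeated looks. The supplied text fixes none of these. A DMC following it could recommend stopping for benefit on either of two outcomes, in an open-label trial, with only the general 0.05 level to refer to.

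Two things are at stake. If 0.05 were reused at an interim look, the chance of a false positive would exceed the nominal 5%. Trials that claim benefit would also, on average, report a somewhat larger effect than they would without the look.

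**Working it through.** **1. The plan's sample size.** Inputs from 9.1: 13.9 days on tacrolimus, target below 10 days (difference taken as 3.9), and +/- 7 read as an SD. The significance level 0.05 is from 9.2 and taken as two-sided. Power is not stated; 80% is assumed.

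- n per arm = 2 × 7² × (1.960 + 0.842)² / 3.9² = 50.6, so 51, against the planned 50.
- Power with 50 per arm: 3.9 / (7 × √(2/50)) = 2.786, and Φ(2.786 − 1.960) = 79.6%. The t-based figure is 78.8%.

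The planned 100 patients thus fit one final test at two-sided 0.05, with no allowance for interim testing.

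**2. Look times.** The plan gives annual meetings and says that patients "will be enrolled over a period of 2 years" (section 6). The times as fractions of the data are therefore assumed. One look about half-way is the most natural reading: a second meeting near month 24 would come when enrolment is essentially complete.

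**3. Type I error if p < 0.05 were the stopping rule.** Assumed rule: by-arm comparison, stop only if Z₁ > 1.96 in favour of Envarsus XR, otherwise a final two-sided test at 0.05. Under the null, the correlation of Z₁ and Z₂ is √t₁, or 0.707 at half-way.

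- Overall error = 0.05 + P(Z₁ > 1.96 and |Z₂| ≤ 1.96) = 0.05 + 0.0166 = 0.0666.
- False claim of benefit = 0.025 + 0.0166 = 0.0416.

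| Assumed looks | Overall type I error |
|---|---|
| None | 5.0% |
| 95% | 5.5% |
| 80% | 6.0% |
| 50% | 6.7% |
| 45% and 95% | 7.1% |
| 25% and 75% | 8.0% |
| 10% and 60% | 8.5% |
| 10% and 50% | 8.65% |

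Section 9.2 also allows a Wilcoxon test. With skewed (gamma) data of mean 13.9 and SD 7, one half-way look gives 6.6%, so the choice of test hardly matters.

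**4. With a boundary.** Haybittle-Peto (p < 0.001 at the look, 0.05 at the end) gives 5.0% for the 50% and the 25%/75% schedules. An O'Brien-Fleming-type boundary at half-way uses nominal levels of 0.0052 and 0.0480 and also gives 5.0%.

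**5. Planned effect (simulation; difference 3.9, SD 7, 50 per arm, t-test, look at 25 per arm).**

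| Rule at half-way | Stops there | Mean estimate at stop | Power | Mean estimate, all trials claiming benefit |
|---|---|---|---|---|
| No look | – | – | 79% | 4.4 days |
| p < 0.05 in favour | 49% | 5.5 days | 81% | 4.8 days |
| p < 0.001 in favour | 8% | 7.4 days | 79% | 4.6 days |

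The last column weights trials that stop early and trials significant at the end:

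- p < 0.05: (0.487 × 5.48 + 0.323 × 3.84) / 0.809 = 4.8.
- p < 0.001: (0.076 × 7.41 + 0.712 × 4.28) / 0.788 = 4.6.

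**The case against.** The strongest reply is that a DMC charter is a natural home for a stopping boundary, and the charter and DSMP were not supplied. That stands. What can be shown is that 9.4 and 11.6 neither state a boundary nor point to one.

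Secondly, no section says that p < 0.05 applies at a DMC review. Section 9.2 gives a general level, and 6.7.1 and 11.5 list circumstances that may justify stopping without tying them to the annual report. This stands too: a reader might infer that the trial is planned to run at an inflated error rate, and the documents do not support that. The 6.7% shows what the silence permits. Error would also stay close to 5% if the committee used a strict threshold of its own. Section 11.6 does not say whether outcomes are shown by arm, and a pooled report would not inflate error.

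Thirdly, the looks may be meant as descriptive. Section 11.6 gives integrity and conduct as the purpose, and the synopsis speaks of description and trends. That is a fair reading of those passages, but it leaves unexplained why efficacy is twice listed as a ground for stopping.

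Finally, a reader might set the 5.5 days seen in trials stopped half-way at p < 0.05 against the 4.4 days among significant full-size trials. That compares a subset with a whole. Across all trials claiming benefit, the figures are 4.8 and 4.4 days.

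**Conclusion.** The gap is real and should be closed, but it is a gap in the text and not a demonstrated loss of error control. An efficacy stop is listed, the primary outcome is scheduled for annual review, and the supplied text gives no criterion and conflicting statements of which outcome is primary.

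If p < 0.05 were used by arm at one half-way look, in favour of Envarsus XR only, overall type I error would be about 6.7% and false claims of benefit about 4.2%, against 5% and 2.5%. Other assumed look times give about 5.5% to 8.65%; these illustrate and do not bound the effect. Under the planned effect, the average claimed benefit would rise by about 0.4 days (4.8 against 4.4), of which a p < 0.001 rule would remove a little over half.

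These figures rest on the assumed stopping rule and look times, a by-arm report, and +/- 7 being an SD. Confidence is medium, because the charter or DSMP may already settle the matter.

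**What to change.** 1. Correct 9.3 so that duration of DGF is the primary analysis and dose adjustments are secondary, matching 5.1.1, 5.1.2 and 9.1.
2. In 9.4, do one of the following and cross-refer to it from 6.7.1, 11.5 and 11.6:
   - State that DMC outcome reports are descriptive, and delete the efficacy ground from 6.7.1 and 11.5.
   - Allow an efficacy stop only at two-sided p < 0.001 in favour of Envarsus XR on duration of DGF, with the final test at two-sided 0.05 (Haybittle-Peto), or use an equivalent boundary that preserves the 5% level.
   - Cite the boundary, if the charter or DSMP already holds one.
3. In 11.6, say whether the outcome analysis is by arm or pooled.

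The cost is a few sentences, with no added patients or data; with the p < 0.001 rule, power stays at about 79%. The downside of that rule is that an early efficacy stop becomes less likely: about 8% instead of 49% at half-way under the planned effect. An estimate at such a stop would still be exaggerated, averaging about 7.4 days against a true 3.9.
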